6.4 Administrative/Other Procedures

6.4.1 Subject Withdrawal/Discontinuation Criteria: Subjects may withdraw consent at any time for any reason or be dropped from the trial at the discretion of the investigator should any untoward effect occur. In addition, a subject may be withdrawn by the investigator if enrollment onto the trial is inappropriate, if the trial plan is violated, or for administrative and/or other safety reasons.

A subject must be discontinued from the trial for any of the following reasons:

- The subject or legal withdraws consent.
- Inter-current illness that prevents further monitoring.
- Investigator's decision to withdraw the subject.
- The subject has a confirmed positive serum pregnancy test.
- Noncompliance with trial treatment or procedure requirements.
- The subject is lost to follow-up.

Additional subjects may be enrolled on an as-needed basis to substitute for patient's removed prior to the first follow up visit after chemoradiation.

6.4.2 Adverse Event (AE) Monitoring: The investigator or qualified designee will assess each subject to evaluate for potential new or worsening AEs as specified in the Trial Flow Chart and more frequently if clinically indicated. Adverse experiences will be graded and recorded throughout the study and during the follow-up period. Toxicities will be characterized regarding

seriousness, causality, grading, and action taken with regard to trial treatment. Grading will be determined utilizing CTCAE v. 4.0.

6.4.3 Trial Database: All data on trial including toxicities, demographics, medical history, and treatment response will be entered into a trial-specific REDCap database.

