7.2 Enrollment

Anticipated enrollment is 1 patient every other month. We should be able to enroll 48 evaluable patients over 8 years. We anticipate 8 patients may not be evaluable such that we will have a total of 40 evaluable patients on this trial. Following enrollment of the last patient, we anticipate 6 months of follow up to obtain adequate toxicity data for the primary endpoint. Thus, we anticipate that this trial will take approximately 6-8 years to complete.

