7.3 Evaluability

To be evaluable for toxicity, patients must have at least one weekly assessments of adverse events (CTCAEv4).

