where λ and α are design parameters optimized to minimize the chance of incorrectly claiming that a safe treatment is unacceptable under the alternative hypothesis $H_1: p_{tox} = 0.3$, while controlling the type I error rate at 0.1 (i.e., the chance of incorrectly claiming that an overly toxic treatment is acceptable is no more than 10%). Assuming a Beta (0.5,0.5) prior distribution for p_{tox} , the above decision rule corresponds to the following stopping boundaries:

Table 3: Optimized stopping boundaries

# patients treated	Stop if # toxicity >=
10	7
20	11
30	14
40	16

Based on Table 3, we perform the interim analysis when the number of enrolled patients reaches 10, 20, 30. When the total number of patients reaches the maximum sample size of 40, we reject the null hypothesis and conclude that the treatment is acceptable if the number of toxicities are less than 16; otherwise we conclude that the treatment is unacceptable. We anticipate we will have to enroll 48 patients to have 40 evaluable patients for this analysis.

Below in Table 4 are the operating characteristics for the safety monitoring based on 10000 simulations using the BOP2 web application, which is available at <http://www.trialdesign.org>.

Table 4: Operating characteristics

Toxicity rate	Early stopping (%)	Claim acceptable (%)	Sample size
0.5	72.70	7.31	26.7

0.4	30.55	42.83	34.9
0.3	4.93	87.57	39.1
0.2	0.17	99.57	40.0
0.1	0.00	100.00	40.0

7.4.2 Secondary Clinical Endpoints:

- Secondary Endpoint #1: *To assess the feasibility of enrolling patients on a prospective trial delivering LET-optimized IMPT for newly diagnosed, non-metastatic anal cancer.*
 - We will assess accrual at 24 months after the study open to determine feasibility of enrolling 40 patients and obtaining insurance approval for IMPT treatment over the planned 9 years.
- Secondary Endpoint #2: *To develop guidelines and workflow to create and deliver anal canal cancer treatments using LET-optimized IMPT.*
 - We will present the results of our workflows in a descriptive manner.
- Secondary Endpoint #3: *To evaluate complete response rate at 12 weeks and 24 weeks post-treatment.*
 - Complete response will be defined as no evidence of disease by physical exam, endoscopy and cross-sectional imaging.
 - Complete response will be reported at 12 and 24 weeks post-treatment as determined clinically by physical exam, endoscopic examination and imaging.

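### The substitution rule in 6.4.1 and the one-assessment evaluability rule in 7.3 are not reconciled, and each can bias the observed toxicity rate downward

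*Combined protocol and SAP*

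**What the plan says.** **Removal and substitution (6.4.1).** A subject may "be dropped from the trial at the discretion of the investigator should any untoward effect occur". Later in the same section: "Additional subjects may be enrolled on an as-needed basis to substitute for patient's removed prior to the first follow up visit after chemoradiation". The reason for removal does not restrict substitution. Nothing is said about whether the removed patient stays in any analysis.

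**Evaluability (7.3).** The whole rule is: "To be evaluable for toxicity, patients must have at least one weekly assessments of adverse events (CTCAEv4". No 12-week visit is needed.

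**Recording (6.4.2).** "Adverse experiences will be graded and recorded throughout the study and during the follow-up period".

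**Numbers (7.2 and 7.4.1).** "We anticipate 8 patients may not be evaluable such that we will have a total of 40 evaluable patients on this trial"; and, for the safety analysis, "We anticipate we will have to enroll 48 patients to have 40 evaluable patients for this analysis".

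**Count at the looks (7.4.1).** At the interims, "we perform the interim analysis when the number of enrolled patients reaches 10, 20, 30". Table 3 is headed by patients treated, and the final look is tied to 40 evaluable patients.

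**Endpoints (7.4.1).** The primary comparison tabulates cumulative toxicity at 12 weeks post-treatment and compares it with matched VMAT controls by McNemar's test. The safety rule counts grade 4 or greater toxicity and states no time window. No analysis set is named, and there is no rule for a patient without the 12-week assessment.

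**The concern.** Removal can be caused by the outcome being measured. A patient with grade 4 toxicity in week 3 who is then dropped is evaluable under 7.3 and replaceable under 6.4.1. If the study team treats the substitute as taking that patient's place, an event is exchanged for a fresh draw. If the team keeps both, Table 3 has no boundary beyond 40. The plan does not say which is meant.

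The second route needs no exclusion. A patient assessed once in week 1, free of events, who then leaves is evaluable and counts as a complete non-event, although most of the period at risk is unobserved.

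Two conclusions are exposed: the safety decision (acceptable if fewer than 16 of 40 have grade 4+ toxicity) and the paired grade 3+ comparison with VMAT. In the latter, a lost or truncated IMPT event removes a pair, or turns it, in the direction that favours IMPT. Removal is at the investigator's discretion in an open single-arm trial, so the rule should not leave room for this.

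**Working it through.** **Inputs.** From 7.4.1: boundaries of 7, 11, 14 and 16 toxicities at n = 10, 20, 30 and 40; null rate 0.5; alternative 0.3; type I error limit 0.10. From 7.2 and 7.4.1: 48 enrolled for 40 evaluable, so 8/48 = 16.7% not evaluable. Assumed, because the documents give no figure: the fraction f of toxic patients replaced and left out, and the fraction g of toxic patients whose event is missed after early exit. I also assume that the safety rule shares the 12-week window of the primary endpoint.

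**Step 1: reproduce Table 4.** Exact binomial recursion over the four looks:

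| True rate | Acceptable, exact | Acceptable, Table 4 | Early stop, exact | Early stop, Table 4 |
|---|---|---|---|---|
| 0.5 | 7.38% | 7.31% | 72.34% | 72.70% |
| 0.4 | 42.81% | 42.83% | 30.84% | 30.55% |
| 0.3 | 87.50% | 87.57% | 5.03% | 4.93% |

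The simulated table is right if every patient is fully counted.

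**Step 2: toxic patients replaced and left out.** With true rate p, the rate among those kept is p(1 − f)/(1 − pf), and the number removed per 40 kept is 40pf/(1 − pf). At p = 0.5:

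| f | Removed per 40 kept | Rate seen | Acceptable, left out at every look | Acceptable, interims count all enrolled |
|---|---|---|---|---|
| 0 | 0 | 0.500 | 7.4% | 7.4% |
| 5% | 1.0 | 0.487 | 9.9% | about 9.3% |
| 10% | 2.1 | 0.474 | 13.2% | about 11.7% |
| 20% | 4.4 | 0.444 | 22.7% | about 16.7% |

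Example for f = 10%: 0.5 × 0.9/(1 − 0.05) = 0.474. The last column is by simulation. It takes 7.4.1 at its word for the interims and lets losses affect only the final 40. The 10% limit is crossed at f of about 5.2% in the fourth column and about 6.5% in the fifth.

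**Step 3: toxic patients missed after early exit.** The patient stays in the denominator as a non-event, so the rate seen is p(1 − g). At p = 0.5, 20 toxic patients are expected among 40:

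| g | Events missed per 40 (20g) | Rate seen | Acceptable |
|---|---|---|---|
| 3% | 0.6 | 0.485 | 10.4% |
| 5% | 1.0 | 0.475 | 12.9% |
| 10% | 2.0 | 0.450 | 20.7% |

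**Step 4: effect of a stricter rule on event-free patients.** If toxic patients always count and 8/48 of event-free patients are incomplete and excluded (assumption), a true 0.30 reads as 0.30/(0.30 + 0.70 × 40/48) = 0.34, and acceptance falls from 87.5% to 72.9%. At a true 0.5 the rate reads as 0.5/(0.5 + 0.5 × 40/48) = 0.545, with acceptance about 2.1%.

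The paired comparison is not quantified, because the plan gives no discordance rates.

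**The case against.** The best defence is that no text excludes anyone. Section 6.4.1 only permits extra enrolment, 6.4.2 has adverse events recorded throughout, 6.4.3 puts toxicities in the trial database, and 7.3 is the only evaluability rule. Read together, a removed patient with recorded toxicity still counts. That stands for the safety count. A reader might infer that the one-assessment rule lets toxic cases leave the denominators; it does the reverse, and keeps them in.

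The defence does not settle how a substitute enters a table that ends at 40, which patients form the matched pairs, or why 8 of 48 should be non-evaluable when a single assessment suffices. A stricter unwritten definition may be in use, but that is inference. Nor does it touch early exit, since events after a patient leaves may go unseen.

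A reader might also infer that the error rate could reach 42.8%, the acceptance probability at a seen rate of 0.4. That needs one third of toxic patients to be replaced (0.5 × 48 × 1/3 = 8), so that the whole non-evaluable allowance consists of toxic cases, with losses at every look. The documents support none of these. Under 7.3 a non-evaluable patient has no weekly assessment, so a recorded on-treatment event would not be among the 8. With interims on all enrolled patients the figure is about 23%, and it cannot exceed about 28% (100% − 72.3% stopped early).

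**Conclusion.** The concern holds as a failure to reconcile two rules, each of which can push the observed toxicity rate down. It does not show that the plan directs toxic patients to be discarded, and Table 4 is not in error.

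The margin is thin. The 10% limit is passed once roughly 5 to 7% of toxic patients are replaced and left out, which is little more than one patient per 40 kept, or once about 3% are missed after early exit, which is less than one patient per 40. These thresholds rest on a true grade 4+ rate of 0.5, a common 12-week window, and loss fractions that are assumptions throughout. For the primary comparison, the direction of the bias is clear if controls are fully followed; its size cannot be derived from the plan.

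The early-exit part follows from 7.3 as written. The substitution part depends on how silence in 6.4.1 is read.

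**What to change.** 1. **6.4.1:** state that a patient who has started treatment and has a qualifying toxicity always stays in the Table 3 count and in the matched comparison, and is never displaced by a substitute.
2. **7.3:** replace the one-assessment rule. A patient is evaluable if a qualifying toxicity has occurred or, without one, if assessments cover the on-treatment period and the 12-week visit. Only event-free, incomplete patients may be replaced. Define qualifying separately for each endpoint: grade 4+ for Table 3, and grade 3+ gastrointestinal, genitourinary or hematologic for the comparison.
3. **7.4.1:** use one count, evaluable patients, at all four looks. Take patients in order of enrolment once each one's status is known, so that events, which are known sooner, are not over-represented. State the window for the safety event.
4. **Sensitivity analysis:** report both toxicity rates in all treated patients with at least one assessment.

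**Cost.** This is wording only; the boundaries and the target of 40 stay. Excluding incomplete event-free patients is conservative and can overstate toxicity, as in step 4 of the working (0.30 reading as 0.34); the sensitivity analysis shows by how much. If more than 8 patients prove non-evaluable, each further one adds about two months at the planned accrual of one patient every other month. Waiting for 12-week status delays an interim decision, but reaching a boundary number of events needs no wait, because the count can only grow.

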6.5 Correlative Analyses

6.5.1 Both traditionally-optimized IMPT and LET-optimized IMPT plans will be generated for each patient enrolled on study. The goal of LET-optimized IMPT is to maximize the LET within the target and minimize it in normal tissues while maintaining the coverage requirements for target volumes and dose volume constraints for OARs expressed in terms of (RBE=1.1) weighted doses. This requirement is imposed to assure safety and for consistency with the current practice. The difference in dose distribution between IMPT and LET-optimized IMPT plans is expected to be minimal to moderate. Even though constraints are fully met, due to possible redistribution of high LET values from normal tissues into target volumes in LET-optimized IMPT plans, for some cases mean dose to surrounding critical organs may be increased. Our goal is to evaluate the safety of such differences in dose distributions.

6.5.2 Blood will be drawn at baseline, weekly during chemoradiation and at the 12-week post-treatment follow up visit as per standard of care (Table 1). WBC, ANC and ALC values will be recorded from the standard of care CBC drawn and their nadirs will be correlated with radiation dose to the pelvic bone marrow.

7.0 STASTICAL PLAN:

7.1 Data Collection, Management and Statistical Summary

Study data will be collected and managed using REDCap (Research Electronic Data Capture) electronic data capture tools hosted at MD Anderson ²⁷. REDCap (<http://www.project-redcap.org>) is a secure, web-based application with controlled access designed to support data capture for research studies, providing: 1) an intuitive interface for validated data entry; 2) audit trails for tracking data manipulation and export procedures; 3) automated export procedures for seamless downloads to common statistical packages; and 4) procedures for importing data from external sources. In the case of multi-center studies REDCap uses Data Access Groups (DAGs) to ensure that personnel at each institution are blinded to the data from other institutions. REDCap (<https://redcap.mdanderson.org>) is hosted on a secure server by MD Anderson Cancer Center's Department of Research Information Systems & Technology Services. REDCap has undergone a Governance Risk & Compliance Assessment (05/14/14) by MD Anderson's Information Security Office and found to be compliant with HIPAA, Texas Administrative Codes 202-203, University of Texas Policy 165, federal regulations outlined in 21CFR Part 11, and UTMDACC Institutional Policy #ADM0335. Those having access to the data file include the study PI and research team personnel. All protected health information (PHI) will be removed from the data when it is exported from REDCap for analysis. All dates for a given patient will be shifted by a randomly generated number between 0 and 364, thus preserving the distance between dates. Dates for each

patient will be shifted by a different randomly generated number. Following publication study data will be archived in REDCap.

General descriptive statistics will be computed to report toxicity and outcome metrics. In addition, descriptive statistics will describe pretreatment patient demographics including age, gender, and performance status as well as disease-related characteristics including disease tumor and nodal stage. All time to event analyses will start from the time of enrollment.

7.2 Enrollment

Anticipated enrollment is 1 patient every other month. We should be able to enroll 48 evaluable patients over 8 years. We anticipate 8 patients may not be evaluable such that we will have a total of 40 evaluable patients on this trial. Following enrollment of the last patient, we anticipate 6 months of follow up to obtain adequate toxicity data for the primary endpoint. Thus, we anticipate that this trial will take approximately 6-8 years to complete.

7.3 Evaluability

To be evaluable for toxicity, patients must have at least one weekly assessments of adverse events (CTCAEv4).

7.4 Statistical Analysis Plan

7.4.1 Primary Clinical Endpoint: *To assess physician-reported acute grade 3 or greater gastrointestinal, genitourinary and hematologic toxicities at 12 weeks post-treatment for patients treated with linear energy transfer (LET)-optimized, intensity-modulated proton therapy (IMPT) and compare to contemporary controls treated with VMAT to determine the feasibility of this outcome for a future randomized trial.*

- At baseline, weekly during treatment, and at the 12 week post-treatment follow up appointment, the treating physician will document physician-assessed acute hematologic, gastrointestinal, genitourinary, dermatologic and other toxicities according to the Common Toxicity Criteria for Adverse Events v-4 (CTCAE v4).
- For each cumulative physician-reported toxicity (hematologic, gastrointestinal, genitourinary, dermatologic and other) at 12-weeks post-treatment, we will tabulate results by type, grade, and attribution and compare with contemporary controls treated with standard of care VMAT-based chemoradiation with 5FU and cisplatin for non-metastatic anal squamous cell carcinoma manually and individually matched for (in order): T-stage, radiation dose, age and gender. We will compare toxicity rates using a McNemar's chi-squared test for paired proportions.
- A separate PA protocol will be submitted to retrospectively review the data from these contemporary controls.
- Subset analyses will be carried out to evaluate the effect of other variables that may also impact toxicity in addition to radiation modality (IMPT vs VMAT).

On RTOG 0529, patients treated with dose-painted IMRT-based concurrent CRT for anal cancer had reported worst overall G3 or greater toxicity rates of 83%. GU/GI G3 or greater toxicity rates were 21%, dermatologic G3 or greater toxicity rates were 23% and hematologic G3 or greater toxicity rates were 58% ⁴.

To ensure an LET-optimized IMPT-based CRT approach is not overly toxic, we will monitor physician-assessed toxicity using the Bayesian optimal phase 2 (BOP2) design ²⁸. Specifically, let n denote the interim sample size and N denote the maximum sample size. Let p_{tox} denote the probability of G4 or greater toxicity and define the null hypothesis $H_0: p_{tox} > 0.5$, representing that the treatment is too toxic. We will stop enrolling patients and inspect the safety data for possible trial termination if

$$Pr(p_{tox} \leq 0.5 | data) < \lambda \left(\frac{n}{N}\right)^\alpha,$$

where λ and α are design parameters optimized to minimize the chance of incorrectly claiming that a safe treatment is unacceptable under the alternative hypothesis $H_1: p_{tox} = 0.3$, while controlling the type I error rate at 0.1 (i.e., the chance of incorrectly claiming that an overly toxic treatment is acceptable is no more than 10%). Assuming a Beta (0.5,0.5) prior distribution for p_{tox} , the above decision rule corresponds to the following stopping boundaries:

Table 3: Optimized stopping boundaries

# patients treated	Stop if # toxicity >=
10	7
20	11
30	14
40	16

Based on Table 3, we perform the interim analysis when the number of enrolled patients reaches 10, 20, 30. When the total number of patients reaches the maximum sample size of 40, we reject the null hypothesis and conclude that the treatment is acceptable if the number of toxicities are less than 16; otherwise we conclude that the treatment is unacceptable. We anticipate we will have to enroll 48 patients to have 40 evaluable patients for this analysis.

Below in Table 4 are the operating characteristics for the safety monitoring based on 10000 simulations using the BOP2 web application, which is available at <http://www.trialdesign.org>.

Table 4: Operating characteristics

Toxicity rate	Early stopping (%)	Claim acceptable (%)	Sample size
0.5	72.70	7.31	26.7

0.4	30.55	42.83	34.9
0.3	4.93	87.57	39.1
0.2	0.17	99.57	40.0
0.1	0.00	100.00	40.0

7.4.2 Secondary Clinical Endpoints:

- Secondary Endpoint #1: *To assess the feasibility of enrolling patients on a prospective trial delivering LET-optimized IMPT for newly diagnosed, non-metastatic anal cancer.*
 - We will assess accrual at 24 months after the study open to determine feasibility of enrolling 40 patients and obtaining insurance approval for IMPT treatment over the planned 9 years.
- Secondary Endpoint #2: *To develop guidelines and workflow to create and deliver anal canal cancer treatments using LET-optimized IMPT.*
 - We will present the results of our workflows in a descriptive manner.
- Secondary Endpoint #3: *To evaluate complete response rate at 12 weeks and 24 weeks post-treatment.*
 - Complete response will be defined as no evidence of disease by physical exam, endoscopy and cross-sectional imaging.
 - Complete response will be reported at 12 and 24 weeks post-treatment as determined clinically by physical exam, endoscopic examination and imaging.
- Secondary Endpoint #4: *To evaluate local progression-free survival, distant metastasis-free survival and overall survival at 24 and 48 months.*
 - Patients will follow up with their treating physician at every 3-6 months per the current standard of care MD Anderson gastrointestinal center follow-up algorithm (Table 2).
 - Local Failure/Progression: Either recurrence of disease in the anal canal following clearance, progression of disease in the anal canal after completion of treatment or persistence of disease in the anal canal for more than 6 months after completion of treatment.
 - Distant Metastatic Failure: the appearance of distant metastatic disease.
 - Disease-Free Survival: measured as time to locoregional failure, appearance of distant metastases or death due to any cause.
 - Overall Survival: measured as time due to death due to any cause.
 - We will estimate LPFS, DMFS, and OS from time of enrollment using the Kaplan-Meier method and report estimates with appropriate 95% confidence intervals.
 - For local and regional failure, the date of failure will be recorded as 6 months after the completion of treatment in the case of persistent, biopsy-proven disease after 6 months status-post completion of all therapy.
- Secondary Endpoint #5: *To evaluate rates of patient-reported acute toxicity, function, distress and QOL at 12 weeks post-treatment.*

- PRO-CTCAE will be collected weekly during treatment and also at the 12 week post-treatment follow up visit
- EQ-5D will be collected at baseline and also at the 12 week post-treatment follow-up visit
- The EORTC QLQ- C30will be collected at baseline and also at the 12 week post-treatment followup visit
- Treatment-Related Stress Questionnaire and the Perceived Stress Scale will be collected at baseline and also at the 12 week post-treatment followup visit
- For female patients:
 - Female Sexual Function Index (FSFI)- 19 question survey validated in cancer survivors will be collected at baseline and also at the 12 week post-treatment followup visit.
- For male patients:
 - International Index of Erectile Function Questionnaire (IIEF) will be collected at baseline and also at the 12 week post-treatment followup visit
- For patient-reported acute toxicity, function, distress and QOL instruments, we will graph and summarize the distributions of scores for each instrument over time noting how many patients have data at each time point. We will analyze the changes over time using mixed effects linear models.

- Secondary Endpoint #6: *To evaluate rates of patient-reported late toxicity, function, distress and QOL every 6 months for 24 months.*
 - PRO-CTCAE, EQ-5D, EORTC QLQ-C30, treatment-related stress questionnaire, perceived stress scale, female sexual function index, and international index of erectile function questionnaire will be collected every 6 months following treatment until 24 months post-treatment.
 - For patient-reported acute toxicity, function, distress and QOL instruments, we will graph and summarize the distributions of scores for each instrument over time noting how many patients have data at each time point. We will analyze the changes over time using mixed effects linear models.

- Secondary Endpoint #7: *To evaluate the value of proton therapy by comparing Time-Driven Activity-Based Costing data from the date of consultation until the date of the 12-week follow up visit post-treatment with contemporary controls treated with VMAT.*
 - TDABC data will be collected for the entire acute episode of care from the date of consultation until the 12-week follow up post-treatment for all patients using previously generated departmental process maps. Costs will be tabulated as either treatment or toxicity-management related.

We will then compare these TDABC data with contemporary controls treated with VMAT (as described above) treated during the same fiscal year.

7.4.3 Exploratory Endpoints:

- Exploratory Endpoint #1: *To compare dose to the pelvic bone marrow, bowel, bladder and genitalia between LET-optimized IMPT, traditionally optimized IMPT and VMAT.*
 - Dosimetric studies will be performed comparing the doses from plans generated using the techniques described above.

- We will record dosimetric differences between conventionally optimized (RBE = 1.1) IMPT plans and LET-optimized IMPT plans for analysis using the Wilcoxon rank-sum test. We will also record how often the LET-optimized IMPT plan is chosen by the treating physician over the conventionally optimized (RBE = 1.1) IMPT plan.
- Exploratory Endpoint #2: *To assess rates of leukopenia, neutropenia and lymphopenia at 12-weeks post-treatment for patients treated with LET-optimized IMPT and compare to contemporary controls treated with VMAT.*
 - We will compare the on-treatment blood count nadirs for patients treated with LET-optimized IMPT with matched historical controls treated with VMAT (as described above). Continuous variables will be compared using a Wilcoxon-Rank-Sum test and corresponding p-values will be reported.
- Exploratory Endpoint #3: *To correlate white blood cell counts (WBC), absolute neutrophil counts (ANC) and absolute lymphocyte counts (ALC) with dose to the pelvic bone marrow for patients treated with LET-optimized IMPT.*
 - For each patient treated with LET-optimized IMPT, mean bone marrow dose and bone marrow V10 will be correlated with WBC, ANC and ALC nadir using the Spearman rank correlation coefficient to evaluate for correlation.
- Exploratory Endpoint #4: *To encourage optional co-enrollment on study 2014-0543 so that tumor DNA, rectal microbiome and MRI imaging-based biomarkers can be assessed for patients receiving LET-optimized IMPT and compared with other patients enrolled on 2014-0543 receiving VMAT-based radiation.*
 - Data from tumor swabs, tumor brushings and rectal swabs will be evaluated on 2014-0543 to identify mutations in cancer related genes enriched during the course of chemoradiation. Changes in tumor gene mutations are also correlated with protein phosphorylation status. Additionally, shifts in the microbiome occurring during the course of chemoradiation in the rectal flora.
 - Data from patients coenrolled on 2014-0543 receiving LET-optimized IMPT will be compared with patients enrolled on 2014-0543 only who receive VMAT-based chemoradiation.
 - We will use descriptive statistics and graphical methods illustrate genomic mutations and rectal flora from baseline at each assessment during chemoradiation (week 1, 3 and 5).

